Hypothesis 3.2: Daytime bright light will be associated with decreased circadian misalignment and increased circadian amplitude (effect size).

BACKGROUND:

Overall Premise: This research project addresses intensive care unit (ICU) delirium which is a significant, modifiable source of ICU morbidity and mortality. Delirium affects 50-80% of patients admitted to the medical ICU (MICU).¹ Delirium is a syndrome of acute cerebral dysfunction with features of a change in baseline mental status, inattention and either disorganized thinking or an altered level of consciousness.² Patient risk factors for ICU delirium include older age, hypertension, dementia, alcohol abuse, and chronic benzodiazepine use.² Critical illness related risk factors for delirium include severity of illness, mechanical and non-invasive ventilation, and high doses of benzodiazepines during ICU admission.^{2, 3} ICU delirium is associated with adverse outcomes such as longer hospital stay, impaired cognition, and increased mortality.⁴⁻¹¹ Additional days of delirium incrementally increase the risk of death and cognitive impairment at one year.^{3, 4} Evidence for the use of any medications to treat delirium is limited. Non-pharmacologic treatments such as sleep promotion have shown promise and are recommended by expert guidelines.^{12, 13} Currently sleep promotion efforts are focused on minimizing overnight sound, light, and care to provide patients with a sleep opportunity.¹⁴ However, there is a lack of attention to the potentially significant contribution of circadian abnormalities to the problem of ICU sleep disruption and consequent delirium.

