 - ii. The protocol will be described to the patient; this description will include an overview of student events they already completed, cover in detail the study intervention and any remaining/future study procedures/events, and cover the risks associated with participation.
 - iii. We will assure study subjects that participation is voluntary and that the decision to continue their participation will have no impact on their current or future care.
 - iv. A copy of the consent document will be provided to the patient.
- f. **Timeline of Study Activities (Fig 2):** Patients will be enrolled within 30 hours of hospital admission and before 12:00 on the day of enrollment which is designated “Study Day 1 (D1).” Actigraphy, delirium monitoring, and light measurement (part of feasibility) will start no later than 12:00 on D1. Actigraphy and light measurement will continue until D5 or MICU discharge whichever is longer. If the patient is discharged from the hospital prior to day 5, all study activities stop upon hospital discharge. Study activities will continue if/when the patient is transferred to the general medical floor if the patient completes at least D2 (13:00) in the MICU. Delirium monitoring will occur until D30 or hospital discharge.

[figure not shown]

Figure 2: Study activities timeline.

APPROACH TO AIMS

Aim 1: Determine the association between ICU day-night light patterns and circadian abnormalities (i.e., circadian misalignment and decreased circadian amplitude).

Rationale: Aim 1 will test our hypothesis that non-circadian ICU light patterns are associated with increased circadian abnormalities as measured by urinary aMT6s. Our approach is to measure light levels (10-second intervals) and aMT6s (1-hour intervals, gold standard) for 72 hours following study enrollment; we will also collect exploratory measures of circadian rhythm, namely, actigraphy and heart rate. We will collect descriptive patient data to allow model adjustment during analysis. We define non-circadian ICU light patterns as abnormally low daytime light levels and abnormally high overnight light levels. We define circadian abnormalities as circadian misalignment and decreased circadian amplitude. The absence of circadian rhythm is an extreme decrease in amplitude (i.e., 100%). *This work will establish if non-circadian ICU light patterns are associated with the development of circadian abnormalities.*

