Expected Outcomes: We expect that a low day/night dose ratio will be associated with increased misalignment and decreased amplitude of urinary aMT6s. We expect that this relationship will remain after controlling for listed confounders. We anticipate that we will see effect modification by sepsis and by OSA risk.

Aim 2: Determine the association between circadian abnormalities and the duration of delirium.

Rationale: Aim 2 will test our hypothesis that increased circadian misalignment and decreased amplitude are associated with more days of delirium. Our approach is to measure days of delirium in the same cohort of 100 patients that have been evaluated for circadian abnormalities in Aim 1. After enrollment, we will check patients twice daily for delirium until hospital discharge. We have selected days of delirium as our metric of delirium severity because it is standard in the field and because studies have shown that additional days of delirium convey additional risk for mortality and cognitive impairment.^{4, 5} We will measure (and control for) total amount of sleep (sleep quantity) and overnight sleep efficiency (sleep quality) via actigraphy. We propose that these metrics of sleep disruption act as potential confounders and/or effect modifiers of the association between circadian abnormalities and delirium. For this project focused upon circadian patterns and sleep disruption rather than detailed sleep architecture (e.g., sleep stages), actigraphy, rather than polysomnography, is the sleep measure of choice. It is our expectation that circadian abnormalities will be associated with increased days of delirium. *This aim will be the basis for investigation of circadian entrainment as a means of treating ICU delirium.*

Research Design: The 100 subjects enrolled in Aim 1 will be examined for the outcome of days of delirium in Aim 2. We will collect the following measures: Circadian measures, actigraphy, and patient characteristics will be collected as described in Aim 1. Delirium: Research staff blinded to patient circadian

status and trained in the CAM-ICU will assess patients for delirium once daily from the time of MICU admission until hospital discharge or hospital day 30.⁴⁸ The CAM-ICU is a guideline recommended, validated delirium detection tool with a sensitivity >93% and a specificity >98%.^{2, 48, 49} We are increasing sensitivity in our study by adding validated daily chart review for delirium.⁵⁰

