Aim 2 Analytic Approach: Circadian measures will be analyzed as in Aim 1. Sleep disruption will include two measures: (1) total amount of sleep, a continuous variable calculated as the number of sleep epochs in a 24 hour period and (2) overnight sleep efficiency, a continuous variable calculated as the percent of epochs scored as sleep between 22:00 and 06:00. Sleep will be based on standard Philips Actiwatch Software algorithms. Days of Delirium will be calculated as the sum of days on which the patient is delirious. Delirium will be considered present if either the CAM-ICU or the chart abstraction is positive for a given calendar day. Patients will be censored at day 30 or at hospital discharge.^{59, 60} Confounder and effect mediator variables: Severity of illness, age, and gender will be treated as in Aim 1. Ventilator use will include invasive and noninvasive positive pressure ventilation and will be quantified as ventilator-free days based on published algorithms.⁶¹ For sedative-hypnotic medications, equivalent daily doses of benzodiazepines and narcotics will be calculated using published algorithms.^{62, 63} Propofol and dexmedetomidine total daily dose will be recorded and included in the models.

Testing for Associations: Multivariable Poisson models will assess the associations between circadian misalignment and amplitude and days of delirium. Models will be adjusted for age, severity of illness, ventilator-free days, dose of sedative medication, and measures of sleep disruption. We will test for modification of the associations between misalignment and amplitude and days of delirium by age, sedative-hypnotic medication dose and measures of sleep disruption. Linearity, serial correlation, and model fit will be addressed as in Aim 1. **Power Calculation:** Patients with delirium on the day of enrollment will be excluded, our effective sample size will be reduced by 20% to 80 participants. Assuming two-sided alpha of 0.05, 90% power, overdispersion of 20%, and a mean of 3 days of delirium,⁴ our sample of 80 allows the detection of a minimal risk ratio of 1.12 for each 60 minutes of misalignment. Under the same assumptions, our sample of 80 will detect a minimal risk ratio of 1.08 for each change of 100ng of aMT6s.⁶⁴

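### Aim 2 declares patients censored at day 30 or discharge but models a raw count of delirious days with no stated exposure time and no rule for in-hospital death

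*Combined protocol and SAP*

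**What the plan says.** Statistical Considerations, Aim 2 Analytic Approach, defines the outcome: "Days of Delirium will be calculated as the sum of days on which the patient is delirious". It continues: "Patients will be censored at day 30 or at hospital discharge". The model follows: "Multivariable Poisson models will assess the associations between circadian misalignment and amplitude and days of delirium". The adjustment set is given as: "Models will be adjusted for age, severity of illness, ventilator-free days, dose of sedative medication, and measures of sleep disruption".

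No offset, person-days, length of stay, days alive or vital status is mentioned. The section refers back to Aim 1 for linearity, serial correlation and model fit, but the Aim 1 model has no exposure-time term either. Ventilator use is "quantified as ventilator-free days based on published algorithms"; how that algorithm scores a death is not written out.

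The end of observation is described in three ways. The Timeline of Study Activities says "Delirium monitoring will occur until D30 or hospital discharge", counting from study day 1. The Aim 2 Research Design has research staff "assess patients for delirium once daily from the time of MICU admission until hospital discharge or hospital day 30". The analysis section says only day 30. None of the three says what happens when a patient dies in hospital.

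**The concern.** Censoring has a meaning in a time-to-event model or in a rate model with person-time. A Poisson model for a summed count has no place for it unless days observed enter the model. As written, a patient who dies on day 3 can contribute at most about 3 delirious days, and one followed to day 30 can contribute up to 30. If half of observed days are delirious (assumed), stays of 3, 10 and 30 days give counts of 1.5, 5 and 15 from the same daily burden.

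The Background links ICU delirium to longer hospital stay and higher mortality. The cohort is a medical ICU population, mainly sepsis and acute respiratory failure, with no severity limit. Observation time is therefore unlikely to be unrelated to illness. Days of delirium is the outcome of Aim 2, and the protocol presents that aim as the basis for later work on circadian entrainment. A risk ratio that could reflect delirium, survival or length of stay would be hard to use for that purpose.

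**Working it through.** **The plan's own figures.** The plan gives no death rate and no hospital-stay distribution, so there is no stated bias to reproduce. The Aim 2 power statement uses a mean count of 3 days and has no term for follow-up time. Its inputs are N = 80, two-sided alpha 0.05, 90% power and 20% overdispersion. With the SDs borrowed from Aim 1 (95 min, 180 ng):

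- ln(RR per SD) = (1.960 + 1.282) × √(1.2 / (80 × 3)) = 0.229
- per 60 min: exp(0.229 × 60/95) = 1.156, against 1.12 stated
- per 100 ng: exp(0.229 × 100/180) = 1.136, against 1.08 stated

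The stated values are not reproduced. That is a separate matter, rests on the borrowed SDs, and carries no weight here.

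**Scale of the illustration.** A ratio of 1.12 per 60 min is exp(ln 1.12 × 95/60) = 1.20 per SD of misalignment. A true daily rate ratio of 1.20 per SD is therefore about the effect the plan aims to detect.

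**Hand calculation (all rates assumed).** Take a discharge hazard of 0.10 per day (mean 10 days), a death hazard of 0.025 per day (mean 40 days) and a cap at day 30.

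- Total exit hazard: λ = 0.125. In-hospital deaths by day 30: 0.2 × (1 − e^−3.75) = 20%.
- Expected count = daily rate × expected days observed, where expected days observed = (1 − e^−30λ)/λ.
- A proportional rise in λ shortens expected days by the factor 1 − 3.75e^−3.75/(1 − e^−3.75) = 0.91 on the log scale. Deaths are 0.2 of exits and discharges 0.8.
- Death hazard ratio 1.5 per SD: ln 1.20 − 0.91 × 0.2 × ln 1.5 = 0.182 − 0.074 = 0.108, so RR 1.11.
- Death hazard ratio 2.0 per SD: 0.182 − 0.91 × 0.2 × ln 2 = 0.182 − 0.126 = 0.056, so RR 1.06.
- No daily effect, discharge hazard ratio 0.8 per SD: −0.91 × 0.8 × ln 0.8 = 0.162, so RR 1.18.

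**Simulation.** Cohorts of 80 (400 per scenario where the number is recorded), Poisson regression with and without a log(days observed) offset, mean stay about 9 to 10 days, mean time to death 40 days. Ranges cover repeated runs.

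| Scenario (per SD) | True daily RR | Raw count | With offset |
|---|---|---|---|
| Death unrelated to exposure | 1.20 | 1.20–1.22 | – |
| Death HR 1.5 | 1.20 | 1.10–1.12 | 1.20–1.21 |
| Death HR 2.0 | 1.20 | 1.04–1.06 | 1.20–1.21 |
| Death driven by severity, severity adjusted | 1.20 | 1.19–1.21 | same as raw |
| Discharge HR 0.8 | 1.00 | 1.14–1.16 | 1.00 |

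The fourth row assumes a severity hazard ratio for death of 2 to 3 and a severity–exposure correlation of 0.3 to 0.5. Without adjustment the raw ratio there was 1.09 to 1.15. In the last row the raw count gave false positives in 22% to 26% of cohorts, and the offset model in 4%. In the first row power was 33% for the raw count and 86% with the offset, because variation in stay adds noise to the count.

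**Per 60 minutes.** A second set (600 cohorts, true 1.12 per 60 min, death hazard 0.01 to 0.03 per day, about 9% to 23% in-hospital deaths) gave the same pattern. The raw ratio was 1.03 to 1.10 with death hazard ratios of 1.25 to 1.5 per 60 min, and 1.16 to 1.24 with discharge hazard ratios of 0.9 to 0.8.

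**The case against.** The strongest defence is that Hypothesis 2 concerns more days of delirium, and total days is the metric the protocol justifies. The raw count estimates exactly that. Calling it biased presumes a daily-rate estimand, and a simulation generated from a daily rate will favour a model with an offset. This stands. It is why the raw count should stay, and why the figures above measure the distance between two estimands rather than an error in the count.

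Second, severity and ventilator-free days are in the model. If they explain the link between exposure and death, little bias remains, as the fourth row shows. Neither is time at risk, however, and whether they suffice cannot be known from the documents.

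Third, the offset has faults of its own. It treats death as uninformative. If delirium prolongs stay, days observed is partly a consequence of the outcome. With a true duration ratio of 1.20, no deaths, and each delirious day adding 0.5 to 1 day of stay (assumed), the raw count returned 1.20 and the offset model 1.13 to 1.15. This also stands.

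Finally, the plan is silent about an offset and does not rule one out. That makes this a gap in specification.

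**Conclusion.** The gap holds. The plan names censoring, gives the model no means of applying it, and has no rule for in-hospital death. The resulting count mixes delirium burden with length of observation.

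A reader might infer that early deaths must pull the association toward none, or reverse it. The documents do not support that. The Background says that "Additional days of delirium incrementally increase the risk of death and cognitive impairment at one year"; this links delirium to death at one year, not circadian abnormality to death in hospital within 30 days. Attenuation needs death to rise with circadian abnormality beyond the adjusted covariates. Slower discharge acts in the opposite direction and has at least as much support, since the Background associates delirium with longer stay. No simulated ratio fell below 1; the lowest was 1.03.

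The size rests entirely on assumed death and discharge rates. Depending on them, a true daily ratio of 1.20 per SD could appear as low as about 1.04 or be left unchanged, and a null daily effect could appear as about 1.14 to 1.16. The specification gap is certain; its direction and size are not.

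**What to change.** Keep the raw count and label it the total-days estimand. Prespecify two sensitivity analyses beside it:

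- **(a)** The same Poisson model with offset log(days alive, in hospital and assessed, to day 30), labelled a daily-rate estimand.
- **(b)** Days alive without delirium to day 30, with in-hospital deaths scored 0 and a written assumption for days after discharge, for example counted as alive and delirium-free.

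Report in-hospital deaths and length of stay by level of misalignment and of amplitude, so that readers can see which mechanism is in play. Before computing days at risk, reconcile study D30, hospital day 30 and the unqualified day 30, together with the start of the window. Enrolment requires under 30 hours since hospital admission as of noon, so D1 is hospital day 1 or 2. The end dates therefore differ by at most one day, but the denominator needs a single definition.

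Cost: two further estimands to report, and a few sentences in the plan. Analysis (a) uses in-hospital follow-up only, but treats death as uninformative and can attenuate if delirium prolongs stay. Analysis (b) cannot rest on collected data alone, because delirium monitoring ends at discharge and no later follow-up is described; its result depends on the post-discharge assumption. Neither replaces the planned estimate.

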
Testing for Associations: Because both measures of circadian abnormality (misalignment and decreased amplitude) are continuous and normally distributed, multivariable linear regression models will test for associations, with light dose ratio serving as the exposure. Linearity of the associations will be examined graphically, and higher order terms will be considered as necessary. Models will be adjusted for age, gender, severity of illness, sepsis, risk of OSA, ICU care events per hour, and room temperature variables. We will test for modification of the association between light dose ratio and the outcomes by sepsis and risk of OSA. Because of the non-trivial intra-correlation coefficient expected from the serial correlation of the repeated outcome measures over time, models will employ generalized estimating equations with an auto-regressive correlation structure. Model fit will be evaluated with residual analysis, and significance will be defined as a two-sided p-value ≤ 0.05 . Power Calculations. For both continuous, normally distributed outcomes, power calculations assume a two-sided alpha of 0.05, power of 90%, a sample size of 100, and prevalence of covariates ranging from 20% to 50%. For minutes of misalignment, we further assume a mean of 180 minutes with a standard deviation of 95 and for amplitude a mean of 450 ng with standard deviation of 180.³⁰ Under these assumptions, our sample of 100 is sufficient to detect a range of minimal average shifts between 52-65 minutes of misalignment, and 98-123 ng of urinary aMT6 per

incremental change in the explanatory variables.

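### Aim 2 names a Poisson model for days of delirium but no variance method, although its own power calculation assumes 20% overdispersion

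*Combined protocol and SAP*

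**What the plan says.** All of this is in Statistical Considerations of the combined protocol and SAP.

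- **Outcome (Aim 2 Analytic Approach).** "Days of Delirium will be calculated as the sum of days on which the patient is delirious". Each patient contributes one count.
- **Model (Aim 2, Testing for Associations).** "Multivariable Poisson models will assess the associations between circadian misalignment and amplitude and days of delirium". The models adjust for age, severity of illness, ventilator-free days, sedative dose and sleep measures, and effect modification is also tested. On sedation the Analytic Approach adds: "Propofol and dexmedetomidine total daily dose will be recorded and included in the models".
- **Power (Aim 2).** "Assuming two-sided alpha of 0.05, 90% power, overdispersion of 20%, and a mean of 3 days of delirium", with the sample described as follows: "our effective sample size will be reduced by 20% to 80 participants".
- **Cross-reference (Aim 2).** "Linearity, serial correlation, and model fit will be addressed as in Aim 1". Dispersion is not among the items listed.
- **What Aim 1 supplies.** On correlation, the reason and the method are given together: "serial correlation of the repeated outcome measures over time, models will employ generalized estimating equations with an auto-regressive correlation structure". On fit: "Model fit will be evaluated with residual analysis". No sandwich variance is named, and no step is stated for the case where residuals show excess variance.

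**The concern.** The authors expect the counts to vary more than a Poisson distribution allows, since they powered for it. The model they name does not allow for that by itself. Three things are left open:

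- which standard errors will be used;
- whether the Aim 1 GEE is meant to carry over to an outcome that is not repeated;
- what form the 20% takes, and whether it applies before or after covariate adjustment.

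The error rate of the Aim 2 tests depends on these choices. Intervals that are too narrow would overstate how firmly circadian abnormality is tied to delirium, and the Aim 2 rationale presents this result as the ground for later work on entrainment. Power and analysis could also rest on different variances.

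**Working it through.** **Inputs from the plan.** N = 80, mean 3 days, two-sided alpha 0.05, power 90%, overdispersion 20%. Covariates: age, severity and ventilator-free days (3), sleep measures (2), sedative terms from 1 (a single dose) to 4 (benzodiazepine, narcotic, propofol, dexmedetomidine), so 6 to 9 in all. Gender is listed among the confounders but is absent from the adjustment sentence, and it is not counted here.

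**The plan's own figures.** It states detectable risk ratios of 1.12 per 60 minutes and 1.08 per 100 ng. Aim 2 gives no exposure SD. Carrying over the Aim 1 values (95 minutes, 180 ng) is an assumption. With ratio phi = 1.2:

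- Minimal RR = exp[(1.960 + 1.282) × sqrt(phi / (N × mean × SD²))]
- Misalignment: SD = 95/60 = 1.583, giving sqrt(1.2 / (240 × 2.507)) = 0.0447 and RR = 1.156.
- Amplitude: SD = 180/100 = 1.8, giving sqrt(1.2 / (240 × 3.24)) = 0.0393 and RR = 1.136.

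With phi = 1 the values are 1.141 and 1.123. Neither stated figure is reproduced, so these figures cannot show which form of overdispersion was used. The rest of the check does not depend on them.

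**Model-based Poisson errors.** Let phi be the variance-to-mean ratio left after adjustment. Type I error = 2 × [1 − Φ(1.96/√phi)]; interval shortfall = 1 − 1/√phi.

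- phi = 1.0 (covariates explain the excess): 5.0%, no shortfall.
- phi = 1.1 (half remains): 6.2%.
- phi = 1.2 (all remains): 1.96/1.095 = 1.789, giving 7.4%; shortfall 8.7%.

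**Simulation.** N = 80, mean 3, null exposure, 20,000 replicates per setting, Monte Carlo SE 0.13-0.24 percentage points. The covariates are standard normal with a total log-rate variance of 0.135; both are assumptions, not plan figures. Rejection rates in %, with 6 / 9 covariates and the ratio taken after adjustment:

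| Test and setting | Poisson | Uncorrected sandwich | Leverage-corrected sandwich | Quasi-Poisson, t |
|---|---|---|---|---|
| Main, no excess | 4.8 / 4.8 | 8.0 / 8.6 | 4.5 / 4.0 | 5.0 / 4.9 |
| Main, ratio 1.2 | 7.6 / 7.2 | 8.3 / 8.8 | 4.8 / 4.1 | 5.0 / 5.1 |
| Interaction, ratio 1.2 | 7.6 / 7.5 | 10.1 / 11.0 | 4.5 / 3.9 | 5.1 / 5.2 |

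If 1.2 is the ratio before adjustment, Poisson main tests run at 4.8-5.2% when covariates explain all the excess and at 5.9-6.2% when they explain half.

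**Cost in precision.** At phi = 1.2 the scale factor alone widens intervals by √1.2 − 1 = 9.5%. With the t reference the simulated mean width is 1.11 times the Poisson width, so the widening is about 10-11%. With no excess it is 1.015 times.

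**The case against.** The case on the other side has four parts.

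- **The effect is small on the plan's own figure.** A ratio of 1.2 costs at most about 2.4 percentage points. The covariates were chosen as likely predictors and may absorb some or all of it. This stands and sets the upper end of the size claimed here. A reader might infer a rate near 12% by taking 20% as a negative binomial parameter: variance 3 + 0.2 × 9 = 4.8, ratio 1.6, type I error 12.1%. Nothing in the text points to that reading, so the point should not rest on it.
- **The cross-reference may already answer it.** GEE is commonly fitted with an empirical variance, which does not need the variance to equal the mean. That is a fair reading, so it would be too strong to say that Aim 1 could not apply. But the plan does not say so, and its reason for the GEE is repeated outcomes, which a single total lacks.
- **The sandwich result is conditional.** A reader might infer that sandwich tests exceed 5% at N = 80 in any case. The documents do not support that: the plan names no sandwich, the simulation rests on assumed covariates, and the excess depends on the correction. A degrees-of-freedom correction with a t reference gave 6.5-6.8% for main tests at ratio 1.2, and a leverage correction removes the inflation.
- **Quasi-Poisson is one choice among several.** True. The leverage-corrected sandwich also avoids inflation, and the fix allows for it.

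Aim 2 is also an observational association, and the bright-light pilot is stated not to depend on it. That limits the consequence but does not remove the gap.

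**Conclusion.** The point holds. The model as named is not matched to the variance that the plan itself assumes, and the Aim 1 reference does not clearly repair this. At ratio 1.2, model-based tests run between about 5% and 7.4%, depending on how much of the excess survives adjustment, and intervals are up to 9% too narrow. Under the assumed covariate settings, an uncorrected sandwich gives about 8-9% for main tests. Larger rates for model-based Poisson tests would need a different reading of 20%, or a larger dispersion for which the documents give no figure.

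A reader might also infer that the power statement already pays for the wider intervals, because it mentions overdispersion. That is not established: the stated risk ratios were not reproduced at 1.2, although that check borrows the Aim 1 SDs. The sponsor should confirm it. The change is worth making because it is cheap and settles the variance method before the data are seen; the plan does not show that the analysis will be wrong.

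**What to change.** Replace the Poisson sentence in Aim 2, Testing for Associations, with: *Days of delirium will be analysed by quasi-Poisson regression (log link, Pearson-estimated scale parameter, t reference) for the main and interaction tests. The Aim 1 GEE does not apply to this single count per patient.* An equivalent method valid under overdispersion, such as a leverage-corrected sandwich, is acceptable if it is named in advance.

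In the power statement, say which form of overdispersion was actually used (a variance-to-mean ratio or a negative binomial parameter) and whether it applies before or after adjustment. Do not write in 1.2 unless the calculation used it. Confirm whether the stated risk ratios already allow for the wider intervals.

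The cost is one sentence and one clause, with no new data. Compared with plain Poisson, quasi-Poisson intervals are about 10-11% wider at ratio 1.2 and about 1.5% wider if no overdispersion remains.
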